7.3. Adverse Events

All adverse events will be coded using the MedDRA version 18.1.

For adverse event recording, the study period is defined for each patient as the time period from signature of the informed consent form for this study through the follow-up visit (approximately 7.5 months after the final dose of study drug). Adverse events will be collected at each visit via adverse event inquiry. The onset and end dates, duration (in case of adverse event duration of less than 24 hours), action taken regarding study drug, treatment administered, and outcome for each adverse event must be recorded on the source documentation and transcribed onto the CRF.

The following are considered protocol-defined adverse events to be sent to the sponsor's Global Patient Safety and Pharmacovigilance Department for evaluation: ophthalmic adverse events of at least moderate severity, events of possible drug-induced liver injury (aspartate aminotransferase or alanine aminotransferase $\geq 3 \times$ the upper limit of the normal range [ULN], total bilirubin $\geq 2 \times$ the ULN or international normalized ratio >1.5), Hy's Law events, or events of suspected anaphylaxis and severe hypersensitivity reactions. Severe hypersensitivity reactions will be monitored using the diagnostic criteria for anaphylaxis as outlined by the 2006 Joint National Institute of Allergy and Infectious Disease/Food Allergy and Anaphylaxis Network Second Symposium on Anaphylaxis ([Sampson et al 2006](#)). In the event of suspected anaphylaxis, vital signs, including oxygen saturation and respiration rate, will be measured.

Summaries by treatment group and overall will be presented for treatment-emergent adverse events (overall and by severity), treatment-emergent adverse events determined by the investigator to be treatment-related adverse events (overall and by severity), serious adverse events, protocol-defined adverse events, adverse events causing discontinuation from the study, non-serious treatment-emergent adverse events, and prior to treatment adverse events. Additionally the injection site reactions recorded as adverse events will be summarized by treatment group separately.

The incidence of adverse event will be summarized using descriptive statistics by SOC, PT, and severity of the adverse event. Each patient will be counted only once within a SOC or a PT by using the adverse events with the highest severity within each category. Treatment-related adverse event summaries will include adverse events related to study drug and adverse events with missing relationship to study drug. Adverse events with the missing flag indicating serious will be excluded from the summary of serious adverse events but included in the summary of non-serious adverse events.

Listings for deaths, serious adverse events, adverse events leading to discontinuation, injection site-related adverse events, and protocol-defined adverse events will be presented. All information pertaining to adverse events noted during the study will be listed by subject, detailing verbatim given by the investigator, PT, SOC, date of onset, date of resolution, severity, and relationship to treatment. The onset of adverse events will also be shown relative (in number of days) to the 1st day of treatment. In addition, MedDRA dictionary terms for adverse event descriptions, and adverse event PTs by patient number and treatment group will be presented.

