2.3. Sample Size and Power Considerations

There are no statistical considerations for this sample size. A total of 1842 patients (867 patients from Study TV48125-CNS-30049, 675 patients from Study TV48125-30050, and approximately 300 patients who did not participate in the pivotal efficacy studies) are planned for enrollment, and a 30% drop-out rate is anticipated.

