2.4. Randomization and Blinding

2.4.1. Randomization

This is a randomized study with patients being stratified by gender, country, and preventive medication use at baseline (yes, no) during the pivotal efficacy studies or during this study if they are not rolling over from the pivotal efficacy study.

Patients rolling over from the pivotal efficacy studies who were randomized to the active treatment groups will continue receiving the same treatment throughout the study. Patients rolling over from the pivotal efficacy studies who received placebo and new patients will be randomly assigned in a 1:1 ratio to receive quarterly TEV-48125 at 675 mg or monthly TEV-48125 at 225 mg (Note: Patients with CM will receive a 675-mg loading dosing at visit 2 and TEV-48125 at 225 mg at each subsequent visit.).

Patient randomization codes will be maintained in a secure location within Teva Clinical Supply Chain. At the time of analysis, when treatment codes are needed, the Teva statistician assigned to the study will make a request to unblind and will receive the unblinded codes.

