2.5. Sequence of Planned Analyses

2.5.1. Interim Analyses

In support of a biologics license application (BLA), a cut-off date will be determined for this study and all data accumulated up to the cut-off date will be analyzed. An interim CSR will be prepared on the interim data.

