4.4. Multiple Comparisons and Multiplicity

No inferential analysis will be performed in this study.

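### Adverse events are reported only as crude percentages, with no time at risk and no stated end to the treatment-emergent window, although long-term safety is the primary objective

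*SAP*

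**What the plan says.** - **Measure.** SAP 7.3: "The incidence of adverse event will be summarized using descriptive statistics by SOC, PT, and severity of the adverse event". A patient is counted once per system organ class or preferred term. SAP 4.1 limits categorical summaries to counts and percentages, and protocol 9.7.2 does the same for safety data. Neither document plans a patient-year rate, a time-to-event estimate, or incidence by time interval.
- **Exposure.** SAP 7.2 summarises treatment duration and number of doses in separate tables. Duration ends at the EOT or early-withdrawal day, or at last dose + 27 for patients lost to follow-up. SAP 7.3 gives onset day with the listings.
- **Numbers.** SAP 2.3: "A total of 1842 patients (867 patients from Study TV48125-CNS-30049, 675 patients from Study TV48125-30050, and approximately 300 patients who did not participate" in a pivotal study "are planned for enrollment, and a 30% drop-out rate is anticipated". It adds that "There are no statistical considerations for this sample size".
- **Design.** Placebo rollovers and new patients "will be randomly assigned in a 1:1 ratio" to a monthly or a quarterly active regimen; active rollovers keep their pivotal regimen. Protocol 3.9 describes the study as uncontrolled. SAP 4.4: "No inferential analysis will be performed in this study".
- **Interim report.** SAP 2.5.1 leaves the cut-off date open and says "all data accumulated up to the cut-off date will be analyzed". Protocol 9.12 places this after the pivotal database lock.
- **Recording window.** SAP 7.3 records adverse events from consent to the follow-up visit about 7.5 months after the last dose. It uses the term treatment-emergent without saying when that period ends, and names serious, protocol-defined and discontinuation events without that qualifier.

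**The concern.** With no placebo arm and no inference planned, the absolute frequency of adverse events is the main product of the study. A crude percentage estimates a 336-day risk only if nearly everyone is observed for 336 days and only events in that period are counted. Neither condition is secured: 30% are expected to leave, the interim report will include patients still on treatment, and the counting window may run well past the last dose.

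The events most affected arise late, and those are what a long-term study is meant to find. SAP 7.1 also shows new and placebo-rollover patients apart from active rollovers. If these groups entered at different times, crude percentages at the cut would mix length of observation with risk.

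**Working it through.** **1. The plan's own figures.** 867 + 675 + 300 = 1842, as stated. Treatment is 12 × 28 = 336 days, and the final visit falls on day 308 + 225 = 533, both as scheduled. There is no power figure to reproduce. Completers: 1842 × 0.70 ≈ 1289.

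**2. Final analysis, on-treatment events only.** The timing of drop-out is not given. Assume exponential drop-out reaching 30% at day 336, so c = −ln(0.70) = 0.3567 per 336 days. Mean exposure is 336 × 0.30/0.3567 ≈ 283 days (84%), or 1842 × 282.6/365.25 ≈ 1425 patient-years, against 1694 if all complete.

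For a true 336-day risk p with constant hazard h = −ln(1 − p):

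crude = h/(h + c) × [1 − exp(−(h + c))]

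For p = 10%, h = 0.1054 and crude = 0.1054/0.4620 × (1 − 0.63) = 0.0844, a ratio of 0.84. With drop-out spread evenly instead: 0.70 × 0.10 + 0.30 × (1 − 0.10/0.1054) = 0.0853, a ratio of 0.85.

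Other event patterns, using the mean of exp(−ct/336) over the days when events arise:

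| Events arising in | Crude/true |
|---|---|
| Days 0–28 | (1 − 0.9707)/0.0297 = 0.985 |
| Days 0–336 evenly | 0.30/0.3567 = 0.84 |
| Days 168–336 | (0.8367 − 0.70)/0.1783 = 0.77 |

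**3. Interim cut, on-treatment events only.** The accrual profile and cut date are not given. The planned last visit in 2Q/2018 less 533 days puts the last first dose between 15 October 2016 and 13 January 2017. First patient in is 1Q/2016, and a new patient is dosed about 28 days after entry. First dosing to last first dose therefore spans roughly 198 − 28 = 170 days (5.6 months) to 378 − 28 = 350 days (11.5 months). Simulation with uniform entry over 6 to 11 months and the drop-out of step 2, for a 1% risk:

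| Cut, months after last entry | Mean days on treatment | Crude/true |
|---|---|---|
| 0 | 86–149 | 0.26–0.45 |
| 3 | 165–214 | 0.49–0.64 |
| 6 | 235–257 | 0.70–0.76 |
| 9 | 275–278 | 0.82–0.83 |

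For a rare event the ratio is close to mean days divided by 336 (for example 165/336 = 0.49).

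**4. Counting the whole recording window.** Completers are then observed for 533 days. Mean observation is about 420 days if no withdrawn patient returns for follow-up and about 484 if all do. With the same hazard continuing off drug, the crude percentage for a 1% risk is 1.25 to 1.44 times the 336-day risk (420/336 = 1.25; 484/336 = 1.44).

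**5. Does a rate recover the truth?** In the 10% case of step 2, patients with the event = 1842 × 0.08437 = 155.4. Time at risk to first event or exit = 1842 × (0.37/0.4620) × 336/365.25 ≈ 1357 patient-years. The rate is 155.4/1357 = 11.45 per 100 patient-years, and 1 − exp(−0.1145 × 336/365.25) = 10.0%.

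**The case against.** **The direction is not fixed.** A reader might infer that long-term risk is simply understated. The documents do not support that. Protocol 3.14.4.1 encourages patients who stop treatment to keep attending, withdrawn patients are asked back at 7.5 months, and events are recorded throughout. If all of this counts, the bias runs upward (step 4). This stands, and it is a further reason to define the window.

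**The commonest events are hardly affected.** Protocol 1.4.1.1 names administration-site reactions as the most frequent events. Bias is under 2% for events in the first 28 days, and SAP 7.4 already summarises injection-site assessments by visit among patients injected. This stands for those events, but not for late ones.

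**The interim inputs are assumed.** A reader might also infer that exposure at the cut will be very unequal. Staggered entry is plausible, but its size depends on an unstated date. A cut at last entry looks unlikely: the SAP amendment of 06 April 2017 still leaves the date open, and on planned dates that is 83 to 173 days (about 3 to 6 months) after the last first dose. Actual enrolment is not given, so the later rows of the table are the more credible, without being established.

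**Exposure is visible, and comparisons are protected.** Duration and dose counts are tabulated by group and onset days are listed, and contrasts between regimens suffer less if drop-out is similar. Both are fair. But mean duration does not give time at risk for a given term, which stops at the first event, and the absolute risk stays distorted.

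**A single rate has its own assumption.** Events per patient-year read cleanly only if the hazard is roughly constant. This stands, so interval incidence belongs beside the rate.

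**Conclusion.** The point holds for absolute long-term incidence. On treatment, with constant hazard and 30% drop-out, crude percentages fall about 15% to 16% short in relative terms at the final analysis. The shortfall is about 23% for events arising in days 168 to 336 and under 2% for first-month events. At the interim cut it could be anywhere from about 17% to 74%, on assumed accrual of 6 to 11 months and a cut 0 to 9 months after last entry. If follow-up events are counted, the percentage is instead about 25% to 44% too high as a 336-day risk.

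The plan does not say which of these applies, because it sets no end to the treatment-emergent period. No general claim of understatement follows. The conclusion is that the planned tables cannot be read as a long-term risk without a matched time at risk. It is a worthwhile, inexpensive improvement; the crude tables remain valid as counts.

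**What to change.** - **SAP 7.3:** define the end of the treatment-emergent window, and say whether serious, discontinuation and protocol-defined events are summarised within it.
- **SAP 7.2:** state how patients still on treatment at the cut-off contribute exposure. The present rule covers only EOT, early withdrawal and loss to follow-up.
- **SAP 7.3, both study reports:** beside the crude percentages, give patients with the event per 100 patient-years at risk, with time censored at first event or at the end of the same window. Do this for adverse events, serious adverse events, events leading to discontinuation and protocol-defined events.
- **Key events:** add incidence by time interval with numbers at risk, since one rate assumes a roughly constant hazard.

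The cost is the derivation of time to first event for each term and one rule for ongoing patients. Onset dates and dosing dates are already collected, so no new data are needed.

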- to evaluate the efficacy of sc TEV-48125 in patients with migraine, as assessed by the reduction in the number of migraine days in patients not receiving concomitant migraine preventive medications at baseline
- to evaluate the efficacy of sc TEV-48125 in patients with migraine, as assessed by the reduction in the number of headache days of at least moderate severity in patients not receiving concomitant migraine preventive medications at baseline
- to evaluate the efficacy of sc TEV-48125 in patients with migraine, as assessed by the reduction in the number of migraine days for new patients and placebo-treated rollover patients
- to evaluate the efficacy of sc TEV-48125 in patients with migraine, as assessed by the reduction in the number of headache days of at least moderate severity for new patients and placebo-treated rollover patients
- to evaluate the efficacy of sc TEV-48125 in patients with migraine, as assessed by the reduction of the number of headache days of any severity
- to evaluate the efficacy of sc TEV-48125 in patients with migraine, as assessed by the reduction of the use of any acute headache medications
- to evaluate the efficacy of sc TEV-48125 in patients with migraine, as assessed by the discontinuation of use of concomitant preventive medications
- to evaluate the efficacy of sc TEV-48125 in patients with migraine, as assessed by the reduction of migraine-related disability and change in quality of life
- to evaluate the immunogenicity of TEV-48125 and the impact of ADAs on clinical outcome in patients exposed to sc TEV-48125
- to explore the correlation between pharmacokinetic parameters and drug efficacy
- to explore the relationship between genetic polymorphisms within the CGRP receptor-ligand complex (eg, CALCA, CALCB, CALCRL, CRCP, and RAMP) and migraine-associated genes (eg, PRDM16, AJAP1, TSPAN2, MEF2D, TRPM8, TGFB2, PHACTR1, FHL5, C7orf10, MMP16, ASTN2, LRP1, APOA1BP, TBC1D7, FUT9, STAT6, ATP5B, and MTHFR) and mode-of-action-related pathways versus hypertension, migraine severity, and safety and efficacy responses

- to explore the relationship between biofluid bone, angiogenic, and inflammatory biomarkers with TEV-48125 concentrations and efficacy responses

Study Endpoints:

Primary Endpoints: The safety and tolerability endpoints for this study are as follows:

- occurrence of adverse events throughout the study

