The relationship of each adverse event to study drug and study procedures, and the severity and seriousness of each adverse event, as judged by the investigator, must be recorded as described below.

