7.1.5.3. Reporting a Serious Adverse Event

7.1.5.3.1. Investigator Responsibility

To satisfy regulatory requirements, all serious adverse events (as described in Section 7.1.5.1) that occur during the defined study period (including the protocol-defined follow-up period, described in Section 7.1.2), regardless of judged relationship to treatment with the study drug, must be reported to the sponsor by the investigator. The event must be reported within 24 hours of when the investigator learns about it. Completing the serious adverse event form and reporting the event must not be delayed, even if not all the information is available. The investigator does not need to actively monitor patients for adverse events once this study has ended. Serious adverse events occurring in a patient after the defined study period should be reported to the sponsor if the investigator becomes aware of them.

The serious adverse event form should be sent to the local safety officer (LSO) or other designated personnel (a contract research organization [CRO] in a country without a sponsor LSO; contact information is in the Clinical Study Personnel Contact Information section); the LSO will forward the report to the sponsor's Global Patient Safety & Pharmacovigilance Department.

The following information should be provided to record the event accurately and completely:

- study number
- investigator and investigational center identification
- patient number
- onset date and detailed description of adverse event
- investigator's assessment of the relationship of the adverse event to the study drug (no reasonable possibility, reasonable possibility)

Additional information may include the following:

- age and sex of patient
- date of 1st dose of study drug
- date and amount of last administered dose of study drug
- action taken
- outcome, if known
- severity
- explanation of assessment of relatedness
- concomitant therapy (including doses, routes, and regimens) and treatment of the event
- pertinent laboratory or other diagnostic test data
- medical history
- results of dechallenge/rechallenge, if known

- for an adverse event resulting in death:
 - cause of death (whether or not the death is related to study drug)
 - autopsy findings (if available)

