9.5.1. Primary Endpoint

The primary endpoints for this study are safety-related and are presented in Section 9.7.

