9.7.2. Safety and Tolerability Analysis

All adverse events will be coded using the Medical Dictionary for Regulatory Activities. Each patient will be counted only once in each preferred term or system organ class category for the analyses of safety. Summaries will be presented for all adverse events (overall and by severity), adverse events determined by the investigator to be related to study treatment (ie, reasonable possibility; see [Section 7.1.4](#)) (defined as related or with missing relationship) (overall and by severity), serious adverse events, and adverse events causing withdrawal from the study. Patient listings of serious adverse events and adverse events leading to withdrawal will be presented.

Injection site erythema, induration, ecchymosis, and pain will be assessed, and severity will be graded as described in [Section 7.9](#), and findings will be listed and summarized.

Changes in laboratory and vital signs measurement data will be summarized descriptively. All values will be compared with prespecified boundaries to identify potentially clinically significant changes or values, and such values will be listed.

The use of concomitant medications will be summarized by therapeutic class using descriptive statistics. Concomitant medications will include all medications taken while the patient is treated with study drug.

Safety data will be summarized descriptively overall, by diagnosis, and by treatment group. For continuous variables, descriptive statistics (n, mean, SD, median, minimum, and maximum) will be provided for actual values and changes from baseline to each time point. For categorical variables, patient counts and percentages will be provided. Descriptive summaries of serious adverse events, patient withdrawals due to adverse events, and potentially clinically significant abnormal values (clinical laboratory or vital signs) based on predefined criteria will also be provided.

If any patient dies during the study, a listing of deaths will be provided and all relevant information will be discussed in the patient narrative included in the clinical study report.

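### SAP 7.3 files adverse events with a missing seriousness flag as non-serious, so the serious adverse event summary can be too low or unchanged but never too high; the likely effect is small and cheap to remove.

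*SAP*

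**What the plan says.** SAP Section 7.3 gives two rules for missing adverse event attributes in consecutive sentences.

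- **Missing relationship** is counted as related: "Treatment-related adverse event summaries will include adverse events related to study drug and adverse events with missing relationship to study drug". Protocol Section 9.7.2 agrees, with related events "defined as related or with missing relationship".
- **Missing seriousness** is counted as non-serious: "Adverse events with the missing flag indicating serious will be excluded from the summary of serious adverse events". The same sentence places these events in the non-serious summary instead.

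The protocol has no rule for missing seriousness, so this choice comes from the SAP alone, and the SAP gives no reason for it. SAP Section 13 records no changes to the protocol-specified analyses.

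The rule sits within the main purpose of the study. Protocol Section 9.5.1 says "The primary endpoints for this study are safety-related and are presented in Section 9.7", and the first endpoint listed there is "occurrence of adverse events throughout the study". A summary of serious adverse events is one of the planned presentations of that endpoint (Protocol 9.7.2, SAP 7.3).

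On data collection, Protocol Section 7.1.2 requires that "the severity and seriousness of each adverse event, as judged by the investigator, must be recorded as described below". Serious events also need their own form, and under Section 7.1.5.3.1 "The event must be reported within 24 hours of when the investigator learns about it".

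**The concern.** When a safety attribute is missing, the usual cautious choice is to assume the less favourable value. The SAP does so for relationship and does the reverse for seriousness, without explanation. The serious adverse event table is among the most closely read outputs of a long-term safety study.

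Two features of this study add some weight. First, no inferential analysis is planned (SAP 4.4), and Protocol Section 3.9 describes the study as uncontrolled. The absolute incidence is thus itself the result, and no placebo group is exposed to the same error. Second, a misfiled event may be hard to spot. The fields named for the by-subject adverse event listing in SAP 7.3 do not include seriousness, and nothing requires the number of missing flags to be reported.

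**Working it through.** The documents state no figure for this point, so there is none to reproduce. The check has two parts: direction and size.

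**Direction.** Define, in patients:

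- S: those with at least one event flagged serious
- m: those with no flagged serious event but at least one event whose flag is missing
- k: those among the m whose missing-flag event is truly serious, so 0 ≤ k ≤ m

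Taking the recorded flags as correct:

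| Handling | Patients in the serious summary |
|---|---|
| SAP 7.3 rule | S |
| True value | S + k |
| Missing counted as serious | S + m |

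Hence S ≤ S + k ≤ S + m. The SAP rule is short by k patients, or exact if k = 0. Counting missing as serious is too high by m − k, or exact if k = m. Each patient counts once within a system organ class or preferred term, so a missing flag changes nothing in a category where the patient already has a flagged serious event.

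**Size.** The denominator is the planned enrolment in SAP Section 2.3: 867 + 675 + 300 = 1842, which agrees with the stated total.

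- One affected patient: 1/1842 = 0.05 percentage points.
- Largest shortfall for m = 5: 5/1842 = 0.27 percentage points.
- For m = 0: no shortfall.

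The documents give neither the number of missing flags nor an expected serious event rate. The range m = 0 to 5 and the rates of 1%, 3% and 5% below are assumptions.

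| Assumed flagged rate | S | SAP rule, S/1842 | All 5 missing counted as serious, (S + 5)/1842 |
|---|---|---|---|
| 1% | 18 | 0.98% | 1.25% |
| 3% | 55 | 2.99% | 3.26% |
| 5% | 92 | 4.99% | 5.27% |

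The largest absolute shortfall does not depend on the event rate and grows in proportion to m. As a stress case, m = 20 would give 20/1842 = 1.09 points.

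**What the rule does not touch.** An event with a missing flag is still counted among all treatment-emergent adverse events, overall and by severity. Where applicable, it also stays in the related, discontinuation and protocol-defined summaries. Only the split between serious and non-serious moves.

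**The case against.** The strongest reply is that a truly serious event with a missing flag is unlikely to survive to analysis. Seriousness is a required item. A serious event also generates a separate form, sent to the sponsor within 24 hours and reviewed by both investigator and sponsor (Protocol 7.1.5.3.1). Case report forms are checked for mandatory values, outside data are compared with the database, and discrepancies are queried (Protocol 13.2). On this view the asymmetry may be deliberate. Relationship has no second reporting channel for ordinary adverse events, whereas seriousness does, so a missing flag with no serious event form is some evidence that the event was not serious.

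Most of this stands, and it is why the expected effect is small. It does not justify the rule as written. The SAP does not give this reasoning and does not make the non-serious classification depend on the absence of a serious event form. Protocol 13.2 does not name the serious event database among the outside sources to be compared.

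It is also fair to object that counting every missing flag as serious replaces one one-sided error with another. A mild event with an empty box could enter the serious table with no report behind it. That is a good reason to reconcile first and impute only what remains.

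A reader might infer three stronger points that the documents do not support:

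- **That the primary endpoint is understated.** The endpoint is the occurrence of adverse events, and that count does not change. Only one planned summary of it is affected.
- **That the interim analysis for the licence application is where the rule does most harm.** SAP 2.5.1 and Protocol 9.12 describe a data cut, but neither says the data will be less clean. Late queries are plausible at a cut, but that is inference.
- **That the effect in a treatment arm can be stated.** The documents give no arm sizes for this study, so any per-arm figure rests on an assumed denominator.

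**Conclusion.** The concern holds as a one-directional reporting rule of probably small effect. SAP 7.3 resolves missing seriousness in the favourable direction, opposite to its own rule for missing relationship, and nothing elsewhere in the documents corrects this. The wording and direction of the rule are certain; its impact is not. The result of at most 0.27 points rests on the planned 1842 patients and on the assumption that 0 to 5 patients have a missing flag as their only candidate serious event. If no flags are missing, or none of those events is truly serious, there is no error. No sample size, test or between-group inference depends on it.

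**What to change.** Replace the seriousness sentence in SAP 7.3 with a short procedure:

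1. Before the interim data cut and again before final lock, query every adverse event with a missing seriousness flag and reconcile it with the serious adverse event forms.
2. Count any flag still missing as serious in both the summary and the listing, marked as imputed, and remove the event from the non-serious table.
3. Report how many such events remain.

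The cost is a brief SAP change plus a reconciliation step at each of the two time points. The serious adverse event count may become slightly less favourable. It may also include a few imputed events with no matching serious event report, which is why they should be marked.
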